4.1.1.2.3 Clinical Activity

As of the clinical cutoff date (CCOD) 17 May 2019, efficacy data are most extensive for patients with non-small cell lung cancer (NSCLC; 1636 atezolizumab treated patients enrolled in BIRCH, POPLAR, OAK, IMpower150, IMpower131, GO28625, and the NSCLC cohort of PCD4989g) and patients with metastatic urothelial carcinoma (mUC; 983 atezolizumab-treated efficacy-evaluable patients in studies PCD4989g, IMvigor210, and IMvigor211) who were administered atezolizumab.

Results from studies evaluating atezolizumab as monotherapy in patients with locally advanced or metastatic NSCLC (PCD4989g, FIR, OAK, POPLAR, and BIRCH) single-agent treatment with atezolizumab indicated clinically meaningful overall survival (OS) improvement in the 2L/3L NSCLC intent to treat (ITT) population, in comparison with

standard of care, in both non-squamous and squamous histologies, and across all PD-L1 expression subgroups.

Atezolizumab in combination with chemotherapy and other therapeutic agents was demonstrated to have benefit in the settings of small cell lung cancer (SCLC; IMpower133) and NSCLC (IMpower132).

Clinical benefit was observed in patients with renal cell carcinoma (RCC) with the combination of atezolizumab and bevacizumab in IMmotion151. Additionally, in IMmotion150, a clinically meaningful improvement in IRC-assessed progression-free survival (PFS) was observed with atezolizumab and bevacizumab compared with sunitinib in the IC1/2/3 population, and no difference in treatment effect was observed with atezolizumab monotherapy compared with sunitinib in either the IC1/2/3 or ITT populations.

The study IMpassion130 (WO29522) demonstrated improved OS and PFS in patients with triple-negative breast cancer (TNBC) who were treated with atezolizumab and nabpaclitaxel. Updated PFS analysis results were consistent with the primary analysis, confirming long-term benefit. However, study GO30182 (IMblaze370) did not meet its objectives of improved in OS or PFS versus regorafenib in patients with colorectal cancer (CRC) who were treated with atezolizumab and cobimetinib.

Other available efficacy data suggested that treatment with atezolizumab as a single agent or in combination with other therapeutic agents resulted in anti-tumor activity across a range of other tumor types and hematologic malignancies (including pediatric-type tumors), across lines of therapy, and across PD-L1 expression subgroups.

For further details, see the atezolizumab Investigator's Brochure.

#### 4.1.1.2.4 Clinical Pharmacokinetics and Immunogenicity

On the basis of available preliminary PK data (0.03–20 mg/kg), atezolizumab appeared to show linear pharmacokinetics at doses  $\geq 1$  mg/kg. For the 1-mg/kg and 20-mg/kg dose groups, the mean clearance (CL) and the mean volume at steady state ( $V_{ss}$ ) had a range of 3.20–4.43 mL/kg and 48.1–64.1 mL/kg, respectively, which is consistent with the expected profile of an IgG1 antibody in humans.

The development of ATAs has been observed in patients in all dose cohorts and was associated with changes in pharmacokinetics for some patients in the lower dose cohorts (0.3, 1, and 3 mg/kg). The development of detectable ATAs has not had a significant impact on pharmacokinetics for doses from 10–20 mg/kg. Patients dosed at the 10-, 15-, and 20-mg/kg dose levels have maintained the expected target trough levels of drug despite the detection of ATAs. To date, no clear relationship between detection of ATAs and AEs or IRRs has been observed.

## 4.2 Rationale

Therapies for breast cancer should be guided by biologic features of the tumor, such as expression of steroid hormone receptors and hormone dependence and/or HER2/neu overexpression. Notable examples are the successful use of hormonal therapy (e.g. tamoxifen or aromatase inhibitors) for patients with hormone-sensitive (estrogen receptor [ER] and/or progesterone receptor [PR] expressing) tumors, and the use of trastuzumab (Herceptin™), a monoclonal antibody against HER2/neu, for patients with overexpression of the aforementioned protein. These are excellent examples of where appropriate patient selection is instrumental on the success of these therapies. An issue with triple negative breast cancer is that the key drivers of this disease are not well understood, and thus molecular targets for therapeutic intervention have not been identified.

We have identified distinct subtypes of triple negative breast cancer to better understand potential drivers of disease progression and to help identify potential therapeutic targets. The presence of immune cells and expression of immune checkpoint genes in the IM subtype may identify patient populations that benefit from immune checkpoint inhibitors. In addition, carboplatin may induce an increase in mutational burden, which may increase response to immunotherapy. Considering all of our preclinical data, in this study patients with metastatic TNBC will be randomized to carboplatin with or without atezolizumab. We hypothesize that the combination of carboplatin and atezolizumab will be superior to carboplatin alone in efficacy, as measured by median progression free survival. We anticipate that high levels of pretreatment TILs or the IM subtype will correlate with better outcomes. In addition we hypothesize that the mutational burden in non-synonymous coding mutations will be predictive of response to anti-PD-L1 therapy.

## 5. PARTICIPANT SELECTION

### 5.1 Inclusion Criteria

- Patients must provide informed written consent.
- Patients must be  $\geq 18$  years of age.
- ECOG performance status 0-1.
- Clinical stage IV (metastatic) ER, PR, HER2 negative invasive mammary carcinoma, previously documented by histological analysis and that meets the following criteria:
  - HER2 negativity is defined as any of the following by local laboratory assessment: In-situ hybridization (ISH) non-amplified (ratio of HER2 to CEP17  $< 2.0$  or single probe average HER2 gene copy number  $< 4$  signals/cell), or IHC 0 or IHC 1+ (if more than one test result is available and not all results meet the inclusion criterion definition, all results should be discussed with the Protocol Chair to establish eligibility of the patient)

- ER and PR negativity are defined as  $\leq 10\%$  of cells expressing hormonal receptors via IHC analysis.
- Willing to undergo biopsy of a metastatic lesion (in patients with reasonably accessible metastatic lesions such as chest wall, skin, subcutaneous tissue, lymph nodes, bones, peripheral lung, and liver metastases).
- Measurable disease, defined as at least one lesion that can be accurately measured in at least one dimension by RECIST criteria v1.1.
- Zero or one prior chemotherapy regimens for metastatic disease.
- No prior treatment with carboplatin in the metastatic setting. Carboplatin in neoadjuvant/adjuvant setting may be allowed if prior treatment with carboplatin was completed at least one year prior to initiation of this study and after discussion with the study chair.
- Patients must have adequate hematologic, hepatic, and renal function. All tests must be obtained less than 28 days from initiation of study drug (C1D1). This includes:
  - $ANC \geq 1000/mm^3$
  - Platelet count  $\geq 100,000/mm^3$
  - Calculated creatinine clearance  $\geq 30$  mL/min using the Cockcroft and Gault Formula (see Section 10.2)
  - Bilirubin, SGOT, SGPT, alkaline phosphatase  $\leq 2.5x$  upper limits of normal if no liver metastases present. Serum total bilirubin must be  $\leq 3x$  upper limits of normal for patients with Gilbert disease. Total bilirubin, SGOT, SGPT  $\leq 5x$  upper limits of normal if liver metastases present.
- For patients who are not postmenopausal (women) or surgically sterile (absence of ovaries and/or uterus or vasectomy), agreement to remain abstinent or to use two adequate methods of contraception (e.g., condoms, diaphragm, vasectomy/vasectomized partner, tubal ligation), during the treatment period and for at least 30 days after the last dose of study treatment. Hormone based oral contraceptives are not allowed on study. Postmenopausal is defined as:
  - Age  $\geq 55$  years
  - Age  $\leq 55$  years and amenorrheic for 12 months in the absence of chemotherapy, tamoxifen, toremifene, or ovarian suppression; or follicle stimulating hormone and estradiol in the postmenopausal range
- Subjects must complete all baseline screening assessments. The biopsy may be obtained before or after the patient is deemed eligible by administrative review, but must be before administration of study drugs on cycle 1, day 1.

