### 5.3 Inclusion of Underrepresented Populations

Individuals of all races and ethnic groups are eligible for this trial. There is no bias towards age or race in the clinical trial outlined. This trial is open to the accrual of men and women.

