### 8.2 Concomitant Treatment and Supportive Care Guidelines

#### 8.2.1 Concomitant Therapy

Concomitant therapy includes any prescription medications or over-the-counter preparations used by a patient between the 7 days preceding Cycle 1, day 1 and the treatment discontinuation visit.

Neulasta (pegfilgrastim) may be given prophylactically per treating investigator discretion.

Patients who experience infusion-associated symptoms may be treated symptomatically with acetaminophen, ibuprofen, diphenhydramine, and/or cimetidine or another H2 receptor antagonist, as per standard practice. Serious infusion-associated events manifested by dyspnea, hypotension, wheezing, bronchospasm, tachycardia, reduced oxygen saturation, or respiratory distress should be managed with supportive therapies as clinically indicated (e.g., supplemental oxygen and  $\beta_2$ -adrenergic agonists).

Systemic corticosteroids and TNF $\alpha$  inhibitors may attenuate potential beneficial immunologic effects of treatment with atezolizumab but may be administered at the discretion of the treating physician. If feasible, alternatives to corticosteroids should be considered. The use of inhaled corticosteroids and mineralocorticoids (e.g., fludrocortisone) for patients with orthostatic hypotension or adrenocortical insufficiency is allowed. Megastrol administered as appetite stimulant is acceptable while the patient is enrolled in the study.

Patients who use prophylactic or therapeutic anticoagulation therapy (such as low-molecular-weight heparin or warfarin at a stable dose level), or other allowed maintenance therapy can continue their use. Males and females of reproductive potential should use highly effective means of contraception.

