### 8.4 Cross-over post-progression

Patients who are randomized to carboplatin alone can cross over to receive atezolizumab upon disease progression based on clinical progression or radiographic progression. Patients who are randomized to carboplatin alone and who discontinue carboplatin for toxicity cannot cross over to receive single agent atezolizumab. There may be exceptions to this based on discussion with the Protocol Chair. However, patients on the carboplatin + atezolizumab arm can continue to receive single agent atezolizumab if they discontinue carboplatin due to toxicity. Patients who cross over to receive atezolizumab will follow the assessments and procedures as outlined in the study calendar. The duration of each cycle will continue to be 21

days and the cycle numbers will "reset" to 1 and will be followed by the "X" suffix (e.g., Cycles 1X, 2X, etc.). Crossover therapy (atezolizumab) must begin no later than 21 days after the clinic visit at which progression is determined.

Patients must have labs and procedures performed as outlined in the cross-over study calendar and must meet the values as described in the Inclusion Criteria, prior to receiving atezolizumab based on assessments and procedures performed within 21 days prior to Day 1 of Cycle 1X. Labs and procedures not included in the cross-over study calendar do not have to be repeated. Patients must also agree to a tumor biopsy, as outlined in the eligibility criteria, prior to initiating atezolizumab. Patients will receive crossover treatment until progression, intolerable toxicity, or elective withdrawal from the study. Patients who cross over will be evaluated with radiologic assessments every 3 cycles until disease progression.

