### **8.7 Criteria for Removal from Study**

Patients will be removed from study when any of the criteria listed below apply. All patients who initiate protocol treatment will be included in the overall evaluation of response (intent-to-treat analysis). All reasons for discontinuation of therapy should be documented clearly in the medical record.

If a subject discontinues or withdraws from the study, every reasonable attempt will be made to get a tissue/tumor biopsy, along with blood, at the end of treatment, if the subject is able and willing.

Patients may be withdrawn from the study if they experience any of the following:

- Disease progression, per investigator assessment by RECIST (or irRECIST for atezolizumab arm)
- Intolerable toxicity to atezolizumab or carboplatin. Patients assigned to carboplatin + atezolizumab who experience toxicity to atezolizumab or carboplatin can continue on study with single agent carboplatin or atezolizumab, respectively, at the discretion of the treating physician. Patients will be followed for disease progression and should continue radiologic assessments every 3 cycles as per the study.

Other reasons for patient discontinuation may include, but are not limited to, the following:

- Non-compliance with the study protocol, including, but not limited to not attending the majority of scheduled visits. The Protocol Chair will determine when non-compliance should lead to removal from study. Note: The patients will still be included in the overall evaluation of response (intent-to-treat analysis).
- Patient personal decision. The reason for discontinuation from the study must be documented. The patients will be included in the overall evaluation of response (intent-to-treat analysis) if any protocol therapy was administered prior to withdrawal.
- If the patient becomes pregnant
- Patient is lost to follow-up
- Study is terminated for any reason

The investigator has the right to discontinue a patient from the study for any medical condition that the investigator determines may jeopardize the patient's safety if he or she continues in the study; for reasons of noncompliance (e.g., missed doses, visits); or if the investigator determines it is in the best interest of the patient. The Protocol Chair should be notified in such cases.

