### 13.5.8 Pregnancies in Female Partners of Male Patients

Male patients will be instructed through the ICF to immediately inform the investigator if their partner becomes pregnant during the study or within 90 days after completing treatment with atezolizumab. Male patients who received study treatment should not attempt to father a child until after this 90 day period. A Pregnancy Report should be completed by the investigator immediately (i.e., no more than 24 hours after learning of the pregnancy) and submitted to the VICC Coordinating Center for processing. Attempts should be made to collect and report details of the course and outcome of any pregnancy in the partner of a male patient exposed to study drug. The pregnant partner will need to sign an Authorization for Use and Disclosure of Pregnancy Health Information to allow for follow-up on her pregnancy. Once the authorization has been signed, the investigator will update the Pregnancy Report with additional information on the course and outcome of the pregnancy. An investigator who is contacted by the male patient or his pregnant partner may provide information on the risks of the pregnancy and the possible effects on the fetus, to support an informed decision in cooperation with the treating physician and/or obstetrician.

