#### 13.6.3 Genentech

The Sponsor-investigator must report all SAEs to Genentech within the timelines described below. The completed MedWatch or comparable SAE form should be faxed or emailed immediately upon completion to Genentech Drug Safety at:

[contact] or [contact]

[name]

Relevant follow-up information should be submitted to Genentech Drug Safety as soon as it becomes available

Additional reporting requirements to Genentech include the following:

- Any reports of pregnancy following the start of administration with the atezolizumab and within the follow-up period (for female patients within one year after the last dose of atezolizumab or the partner of a male patient within three months of completing therapy) This includes reports of abortions and congenital anomalies /birth defects. Pregnancies will be followed up until the outcome of the pregnancy is known, whenever possible, based upon due diligence taken to obtain the follow-up information.
- All non-serious atezolizumab AEs originating from the study will be forwarded Genentech quarterly.

Note: Investigators should also report events to their IRB as required.

In addition to SAEs, pregnancy reports and AESIs, the following safety reports should be collected and transmitted to Genentech/Roche even in the absence of an Adverse Event within thirty (30) calendar days:

- Data related to product usage during pregnancy or breastfeeding

- Data related to overdose, abuse, misuse, inadvertent/erroneous administration, medication error or occupational exposure, with or without association with an AE/SAE unless otherwise specified in the protocol
- Data related to a suspected transmission of an infectious agent via a medicinal product (STIAMP)
- Lack of therapeutic efficacy

In addition, reasonable attempts should be made to obtain and submit the age or age group of the patient, in order to be able to identify potential safety signals specific to a particular population

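### For men given atezolizumab, the 30-day contraception minimum ends before the 90-day no-fathering instruction does; for women, the 90-day pregnancy-reporting instruction ends well before the supplier's one-year window

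*Combined protocol and SAP*

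**What the plan says.** **Men.** Section 5.3 states "This trial is open to the accrual of men and women". The contraception criterion in section 5.1 covers men, because it exempts those with a vasectomy, and it runs "during the treatment period and for at least 30 days after the last dose of study treatment". Section 8.2.1 adds "Males and females of reproductive potential should use highly effective means of contraception", with no duration. Section 13.5.8 asks a male patient to report a partner's pregnancy during the study or "within 90 days after completing treatment with atezolizumab", and continues: "Male patients who received study treatment should not attempt to father a child until after this 90 day period". Section 13.6.3, on reports to the supplier, uses a matching period for partners: "or the partner of a male patient within three months of completing therapy".

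**Women.** Section 13.5.7 instructs women of childbearing potential to tell the investigator of a pregnancy that occurs on study or up to 90 days after the last study drug dose. Section 13.6.3 asks for pregnancy reports to the supplier for one year after the last atezolizumab dose.

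**Who is exposed.** Combination-arm patients are exposed from the start. Control patients can be exposed later: "Patients who are randomized to carboplatin alone can cross over to receive atezolizumab upon disease progression". Section 8.7 lets a combination patient who has toxicity from one drug stay on the other; such patients "can continue on study with single agent carboplatin or atezolizumab, respectively, at the discretion of the treating physician". The last dose of study treatment can therefore fall after the last dose of atezolizumab.

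**The concern.** The period a man agrees to at entry is shorter than the period in which he is later told not to father a child. Avoiding an attempt to conceive is also a weaker duty than using contraception. A man who stops contraception on day 31 without intending a pregnancy has met section 5.1, and arguably section 13.5.8, yet his partner could conceive inside the protected period.

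For women the issue is capture. The sponsor-investigator can forward only the pregnancies it hears about, and the instruction that would bring them to the site stops long before the supplier's window closes. At stake are protection against fetal exposure and completeness of pregnancy follow-up. No efficacy result is affected.

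**Working it through.** The plan states no figure for either gap, so the check compares the time limits directly.

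**Set-up.** Day 0 is the last atezolizumab dose, taking completion of atezolizumab treatment to mean that dose. Let k be the number of days carboplatin continues afterwards. k = 0 for combination patients whose last dose includes atezolizumab, and for crossover patients, whose calendar in section 7.2 lists atezolizumab alone.

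**Men.** The section 5.1 minimum ends on day k + 30. The section 13.5.8 instruction ends on day 90. Gap = max(0, 90 − (k + 30)) = max(0, 60 − k).

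**Women.** The section 13.5.7 instruction ends on day k + 90. The section 13.6.3 window ends on day 365. Gap = max(0, 365 − (k + 90)) = max(0, 275 − k).

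| Carboplatin after last atezolizumab | k (days) | Gap, men (days) | Gap, women (days) |
|---|---|---|---|
| None | 0 | 60 | 275 |
| One 21-day cycle | 21 | 39 | 254 |
| Two cycles | 42 | 18 | 233 |
| Three cycles | 63 | 0 | 212 |
| Six cycles | 126 | 0 | 149 |

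**Partners of male patients.** Three months is about 91 days, which agrees with 90. The reporting gap therefore concerns women only.

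**Does a scheduled contact close the women's gap?** Under sections 7.1 and 8.6, contacts for all patients come at about day 30 and then yearly from the last study drug. At k = 0 that means about days 30 and 365, with none in days 91–364. The yearly contact (section 7.1, footnote n) may be a phone call or chart review, and lists survival status and adverse events of special interest, not pregnancy. Only patients with an ongoing serious event, or an event that led to discontinuation, are followed every 3 months (section 8.6).

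**Do other reporting routes close it?** In part:

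- Section 13.1 asks participants to report serious, possibly related post-study events.
- Sections 13.5.9 and 13.5.10 make spontaneous abortion and congenital anomaly serious adverse events, with no stated cutoff.
- Section 13.5.13 sets a forwarding deadline from the date of awareness, but gives the site no means of becoming aware.
- Section 13.5.13.1 covers later anomalies in offspring that the investigator learns of.

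What remains is mainly uncomplicated pregnancy. Section 13.5.7 says pregnancy is not recorded as an adverse event, while section 13.6.3 still wants it reported and followed to outcome.

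**The case against.** The strongest reply is that nothing here conflicts. The 30 days is a floor, set in a criterion applied before allocation or crossover is known, so a rule that is the same for both arms is a reasonable choice there. The rule specific to atezolizumab is in section 13.5.8, is longer and is in force; a man who follows both sections is protected. Section 13.5.8 also says men are instructed through the consent form. If that form carries the 90-day advice, only a difference of wording remains.

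For women, the two provisions do different jobs. One instructs the patient; the other is a duty to forward reports that arrive, and a forwarding window may properly be wider. The year-1 contact can look back over the whole interval, so the absence of a visit inside days 91–364 does not make that period unobserved. The day counts measure wording, not numbers of affected patients.

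Much of this stands. There is no contradiction, the consent text could not be seen, and the count of affected patients is unknown. It does not close either gap. The section 5.1 agreement requires nothing of a man after its minimum ends, and section 8.2.1 supplies no duration. The year-1 contact could reveal an earlier pregnancy, but pregnancy is not among its listed items. Reading the on-study period in section 13.5.7 to include yearly follow-up would make its added 90 days redundant, so that reading is weak.

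**Conclusion.** The point holds as a minor lack of alignment in safety provisions. When atezolizumab is the last study drug, the gap is 60 days for men and 275 days for women. Each day carboplatin continues beyond atezolizumab takes a day off both, and they close at 60 and 275 days respectively.

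This rests on counting from the last atezolizumab dose and on taking one year as 365 days. Carboplatin-only patients who never cross over are outside it. For carboplatin-only men the coverage of section 13.5.8 is itself ambiguous, because the sentence refers to study treatment in general but its 90-day clock starts from atezolizumab. The 30-day contraception minimum for women is not questioned. The documents give no number of men or of women of childbearing potential, so no count of affected patients is offered.

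**What to change.** In section 5.1, keep the existing 30-day minimum and add, for male patients who received atezolizumab, a minimum of 90 days counted from the last atezolizumab dose. This keeps the starting point used in section 13.5.8 and works whichever arm a man is allocated to. The sponsor could instead choose 90 days after any study treatment for all men; that is simpler and more conservative, but goes beyond the current text.

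In section 13.5.7, keep the 90-day instruction and extend it, for women who received atezolizumab (including after crossover), to one year from the last atezolizumab dose. Bring the consent form into line if it differs.

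The cost is one sentence in each of two sections, plus any consent change. Exposed men carry a contraception minimum up to 60 days longer, which section 13.5.8 already implies. Exposed women carry a reporting instruction up to 275 days longer. Design, endpoint and sample size are unchanged.
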